3.2 Sample Size

Thirty adult subjects will be prospectively enrolled in the study. Potentially eligible subjects presenting for onychomycosis treatment at the clinic will be invited to participate in the study and may be included so long as they give informed consent to participate and meet inclusion and exclusion requirements. Investigators will be asked to document all subjects approached for the study by maintaining a prescreening log.

Enrollment will be paused after five subjects are enrolled. Once safety and efficacy data from mycology results from study visit 4 is obtained for all 5 subjects, an interim evaluation will be performed. If the interim evaluation shows safety concerns, the study will be suspended for all subjects pending an assessment of the safety event(s) and appropriate action to prevent the event(s) from reoccurring. If the interim evaluation shows no safety concerns, the enrollment of subjects will resume and the subjects already enrolled will complete the remainder of their study visits per protocol.

4 Populations To Be Analyzed

All enrolled subjects will be included for evaluation.

5 Planned Analyses

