5.2 Handling of Dropouts or Missing Data

Original data will be presented in the data listing. No data manipulation will be applied for dropouts or missing data.

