5.5 Efficacy Variables and Evaluations

Mycological cure is defined as an achievement of negative culture results for both *Trichophyton rubrum* and *Trichophyton mentagrophytes* from both Visit 3 and Visit 4. It will be summarized using frequency and percentage.

All the efficacy data will be presented in subject data listings.

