6.1 Handling of Missing or Incomplete Dates for Adverse Events and Concomitant Medications

Adverse Events

Handling of partial dates is only considered for the start date. An adverse event with a partial start date is considered treatment emergent if:

- only the day is missing and the start month/year is the same or after the month/year of the first dose
- the day and month are missing and the start year is the same or greater than the year of the first dose date

- the start date is completely missing

Concomitant Medications

Handling of partial dates is only considered for the stop date. A medication with a partial stop date is considered concomitant if:

- only the day is missing and the stop month/year is the same or after the month/year of the first dose
- the day and month are missing and the stop year is the same or greater than the year of the first dose date
- the stop date is completely missing or the medication is ongoing

7 Tables and Listings

The following is an example of tables and listings that will be included in the clinical study report. Tables and listings may be modified as needed during the data analyses.

Summary Tables

Table 14.1 – Summary of Mycological Cure

		RenewalNail
All subjects	Subjects who completed both Visits 3 and 4	XX
	Subjects with mycological cure	XX (XX.X%)
Subjects who met the entrance criteria	Subjects who completed both Visits 3 and 4	XX
	Subjects with mycological cure	XX (XX.X%)

Mycological cure is defined as an achievement of negative culture results for both *Trichophyton rubrum* and *Trichophyton mentagrophytes* from both Visit 3 and Visit 4.

Percentage is based on number of subjects who completed both Visits 3 and 4.

Source: Listing 16.2.6.1

O:\Studies\DeviceFarm\DFCR-0002\Biometrics\Programs\Tables\xxx.sas ran on Month Day, Year at hh:mm on data from Month Day, Year

Table 14.2 - Overall Summary of Treatment Emergent Adverse Events (TEAE)

	RenewalNail (N=XX)
Subjects with at least one TEAE	XX (XX.X%)
Subjects with at least one Serious TEAE	XX (XX.X%)
Subjects with at least one Related TEAE ²	XX (XX.X%)
Subjects with TEAE Leading to Study Treatment Interrupted/Discontinued	XX (XX.X%)
Number (%) of deaths	XX (XX.X%)
Overall TEAEs	
Number of Subjects with at least one Mild TEAE	XX (XX.X%)
Number of Subjects with at least one Moderate TEAE	XX (XX.X%)
Number of Subjects with at least one Severe TEAE	XX (XX.X%)
Number of Subjects with at least one Not Related TEAE	XX (XX.X%)

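### Table 14.1 bases the cure percentage on completers in both blocks, so it can drop known non-cures, and it does not show how many enrolled subjects are left out

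*SAP*

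**What the plan says.** - **Section 3.2:** "Thirty adult subjects will be prospectively enrolled in the study".
- **Section 4:** "All enrolled subjects will be included for evaluation".
- **Section 5.5:** cure means negative cultures for both *T. rubrum* and *T. mentagrophytes* at both Visit 3 and Visit 4. On reporting: "It will be summarized using frequency and percentage". No denominator is named.
- **Section 5.2:** "No data manipulation will be applied for dropouts or missing data".
- **Section 7, Table 14.1:** there are two blocks, 'All subjects' and "Subjects who met the entrance criteria". Each has a count of those who completed both visits and a count with percentage of those cured. The footnote gives the only denominator rule in the SAP: "Percentage is based on number of subjects who completed both Visits 3 and 4". Neither the rows nor the column header carry an enrolled N. The header of Table 14.2 does carry an N.
- **Section 7, introduction:** "Tables and listings may be modified as needed during the data analyses".

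**The concern.** The primary objective concerns mycological cure, and with no inference planned the percentage in Table 14.1 will be read as the main result. Three things are unsatisfactory about it.

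1. **Known non-cures can leave the denominator.** One positive culture for either species is enough to fail the Section 5.5 definition. A subject positive at Visit 3 who does not attend Visit 4 has failed without any imputation, but is not a completer and disappears from the percentage.
2. **The number left out is not shown.** For 'All subjects' a reader could approximate it from the N in Table 14.2. For the entrance-criteria block the full N is in neither summary table and would have to be counted from listings such as 16.2.2.1 and 16.2.2.2.
3. **'Completed' is not defined.** Listing 16.2.1.2 records visit dates, and Listing 16.2.6.1 separately records whether a sample went to the laboratory. A subject who attended without a culture result could be kept as a non-cure or removed, and the SAP does not say which.

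**Working it through.** The SAP states no cure, loss or eligibility rate, so there is no figure of its own to reproduce. Only N=30 (Section 3.2) comes from the document; all other inputs are assumptions.

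**Notation.** c = cures; d = subjects without both visits; k = those among the d with a positive culture at the visit they attended (0 ≤ k ≤ d).

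- Printed rate: c/(N−d)
- All-enrolled rate: c/N
- Ratio of printed to all-enrolled: N/(N−d)
- Rate among subjects of determined status: c/(N−d+k)
- Highest possible all-enrolled rate: (c+d−k)/N, because the k known failures cannot be cures

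**Step 1: 'All subjects' block, N=30, c=15.** The all-enrolled rate is 15/30 = 50.0% throughout.

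| d | Ratio 30/(30−d) | Printed rate |
|---|---|---|
| 0 | 1.000 | 15/30 = 50.0% |
| 1 | 1.034 | 15/29 = 51.7% |
| 2 | 1.071 | 15/28 = 53.6% |
| 3 | 1.111 | 15/27 = 55.6% |

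At d=3 with other cure counts: 6 cures give 6/27 = 22.2% against 6/30 = 20.0%; 24 cures give 24/27 = 88.9% against 24/30 = 80.0%.

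**Step 2: known non-cures, N=30, c=15, d=3.** The table prints 55.6% whatever k is.

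| k | Determined-status rate | Highest possible all-enrolled rate |
|---|---|---|
| 0 | 15/27 = 55.6% | 18/30 = 60.0% |
| 1 | 15/28 = 53.6% | 17/30 = 56.7% |
| 2 | 15/29 = 51.7% | 16/30 = 53.3% |
| 3 | 15/30 = 50.0% | 15/30 = 50.0% |

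With k=2 or 3 the printed 55.6% is higher than any all-enrolled rate the data could support. With k=0 or 1 it lies inside the possible range, which starts at 50.0%.

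**Step 3: entrance-criteria block, assuming 25 qualify and 12 are cured.** The rate over the block is 12/25 = 48.0%. The table prints 12/24 = 50.0%, 12/23 = 52.2% and 12/22 = 54.5% for d = 1, 2, 3.

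**Step 4: meaning of 'completed'.** Take 30 enrolled, 15 cures, 2 missing a visit and 1 attending both without a culture result. If 'completed' means attended, the rate is 15/28 = 53.6%. If it means having a culture result, the rate is 15/27 = 55.6%. The all-enrolled rate is 50.0% either way.

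**The case against.** The basis is disclosed: the denominator stands in the row above the percentage and again in the footnote. 'All subjects' is paired with an eligibility subset, so the label can fairly be read as contrasting eligibility, not completion. Section 5.1 makes listings the main presentation, and with 30 subjects the omissions can be counted by hand. Listing 16.2.1.2 places Visit 4 at Day 12 ±3 days, so few subjects may be lost. Counting missing results as failures could be called the data manipulation that Section 5.2 rules out.

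Much of this stands. A reader might infer that Table 14.1 contradicts Section 4. The SAP does not support that: Section 4 fixes who is evaluated, not the denominator of a percentage. A reader might also infer that the printed rate overstates the true cure rate. That does not follow in general, because a subject with no positive culture and one visit missing has unknown status; Step 2 shows the printed figure can lie within the possible range.

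What the objection does not answer is the subject positive at one visit and absent at the other. That subject's failure is observed, so Section 5.2 gives no reason to drop it. Stating the rule also does not state how many it excludes. An all-enrolled row need not conflict with Section 5.2 if it is described as a choice of denominator.

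**Conclusion.** The point holds as a minor to moderate reporting matter. The completer rule can remove observed failures from the percentage for the primary objective, and the table hides the number excluded. Where anyone is excluded and at least one subject is cured, the printed rate exceeds the all-enrolled rate by the factor N/(N−d): 1.034 for one exclusion in 30 and 1.111 for three. With no exclusions nothing changes. The sizes rest on assumed values of c, d and k, and the early Visit 4 suggests a small gap. No hypothesis test or stated threshold depends on the figure. The data themselves are not lost, since the listings hold them.

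**What to change.** In each block of Table 14.1:

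- Print the enrolled N and the number without culture results at both Visit 3 and Visit 4.
- Add a labelled row of cures divided by all enrolled subjects in that block, with the remainder described as 'cure not demonstrated'. Say in Section 5.2 that this is a choice of denominator and that no result is imputed.
- Keep the observed-data percentage beside it, but replace 'completed' in the footnote with a definition: subjects whose cure status is determined, meaning culture results at both visits, or a positive *T. rubrum* or *T. mentagrophytes* culture at either.

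The cost is a few rows per block, a revised footnote and one sentence in Section 5.2. No new data are needed, and Section 7 already allows the shells to change; the wording is best settled before results are reviewed. There are two downsides. The all-enrolled rate may look less favourable than the completer rate, by the factor (N−d)/N. The determined-status rate can also run low, because a single positive settles a subject's status while a single negative does not. Showing both rates with the counts lets the reader judge.

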3.1 Study Design

This is an early feasibility study. It will be conducted as a multi-center open-label study in Subjects who meet the specified inclusion/exclusion criteria. Informed consent will be obtained. Characteristics of subjects including age, gender, disease severity, and disease history will be documented during the screening visit.

Thirty Subjects with 20-75% Distal Subungual Onychomycosis (mild to moderate DSO) infection of their big toe (hallux) nail infected by the dermatophytes *Trichophyton (T.) rubrum* or *T. mentagrophytes* will be enrolled. Enrollment will be paused after the first five Subjects are enrolled. These five Subjects will serve as a sentinel group to monitor treatment safety and efficacy for this group prior to enrolling the remaining 25 Subjects.

Treatments will be performed at the office of the Investigator as elaborated in the Conduct of Study section from the protocol. The treatment protocol outlines three 45-minute treatments over the course of the first week (within 7 calendar days). Cultures will be collected during screening, after the third treatment and a week after third treatment. A final treatment will be performed in week 7 (i.e. 6 weeks after the initial week of treatment). This final treatment is a

preventative maintenance treatment to minimize potential spore release or reinfection of the toenail during the growth of new nail.

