5.1 Methodological Considerations

Due to the nature of the study and the small number of subjects, no inferential statistical analyses will be performed. The results from this study will be used to determine whether the treatment can achieve mycological cure for onychomycosis subjects fulfilling the inclusion/exclusion criteria.

The data is too small to summarize with descriptive statistics; therefore, Subject listings will be presented. SAS software will be used for all data listings.

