------------------	-----------	----------	------------	------------	-----------------------	----------------------	------	------	-------	-----------

Note: Medications coded using the WHO Drug Dictionary, version xxx.

Day # is calculated from Baseline (Visit 1) Date. Day 1 is the Baseline date while Day -1 is the day prior to the Baseline visit.

O:\Studies\DeviceFarm\DFCR-0002\Biometrics\Programs\Listing\xxx.sas ran on Month Day Year at hh:mm on data from Month Day, Year.

Listing 16.2.5.1 – Nail Photographs for Enrolled Subjects

Site-Subject	Visit	Target Big Toenail?	Photo before debridement?	Debridement performed on target toe?	Thinning nail performed?	Photo before treatment?	Photo after treatment?	Photo uploaded?
--------------	-------	---------------------	---------------------------	--------------------------------------	--------------------------	-------------------------	------------------------	-----------------

O:\Studies\DeviceFarm\DFCR-0002\Biometrics\Programs\Listing\xxx.sas ran on Month Day Year at hh:mm on data from Month Day, Year.

Listing 16.2.5.2 – Nail Notching/Treatment for Enrolled Subjects

Site- Subject	Visit	Notch Measurement		Nail Measurement	New nail growth (mm)*	Plasma treatment performed per instructions?	Treatment Start Time	Treatment End Time	Photo after treatment?	Photo uploaded?
		Re-Notch?	Distance (mm)	(mm)						

*New nail growth = nail measurement at Visit 5/Visit 6 - notch measurement at Visit 1. If at anytime during the study the nail has to be re-notched, then new nail growth = nail measurement at Visit 5/Visit 6 – the last re-notch measurement.

O:\Studies\DeviceFarm\DFCR-0002\Biometrics\Programs\Listing\xxx.sas ran on Month Day Year at hh:mm on data from Month Day, Year.

Listing 16.2.6.1 – Mycological Culture for Enrolled Subjects

Site-Subject	Visit	Sample submit to lab	Mycological Culture							Mycological Culture	Mycological Cure*	
			T. Rubrum	T. Mentag.	No Growth	Bacterial Overgrowth	Other Fungi	Other Dermatophyte	Other			
01-001	Scr	Y	X								T. Rubrum	
	3	Y							Xxxxxx		Other Dermatophyte	Yes
	4	Y				X	X				Bacterial Overgrowth; Other Fungi	Yes
	5				X						No Growth	Yes
01-002												

*Mycological cure is defined as an achievement of negative culture results for both Trichophyton rubrum and Trichophyton mentagrophytes from both Visit 3 and Visit 4.
 O:\Studies\DeviceFarm\DFCR-0002\Biometrics\Programs\Listing\xxx.sas ran on Month Day Year at hh:mm on data from Month Day, Year.

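### Does the Visit 5 row in the Listing 16.2.6.1 shell mean that the mycological cure table misses a later positive culture?

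*SAP*

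**What the plan says.** Section 3.1 gives the culture times: "Cultures will be collected during screening, after the third treatment and a week after third treatment". Read against the visit days in Listing 16.2.1.2, these are screening, Visit 3 and Visit 4. Section 3.2 ties the interim evaluation of the five sentinel subjects to the same last culture: "Once safety and efficacy data from mycology results from study visit 4 is obtained for all 5 subjects". No body text names a later culture.

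Cure is defined once and repeated consistently. Section 5.5, the Table 14.1 footnote and the Listing 16.2.6.1 footnote all require "negative culture results for both Trichophyton rubrum and Trichophyton mentagrophytes from both Visit 3 and Visit 4". Under Table 14.1 the denominator is fixed as well: "Percentage is based on number of subjects who completed both Visits 3 and 4". The table cites its origin as "Source: Listing 16.2.6.1".

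The shell of that listing shows a mock subject with rows for screening and Visits 3, 4 and 5. The Visit 5 row carries a no-growth result and a cure flag of Yes. Its cell for whether a sample went to the laboratory is blank, whereas the other three rows show Y.

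Section 5.5 adds: "All the efficacy data will be presented in subject data listings". Section 5.1 rules out inferential analysis and makes listings the main form of presentation. Section 7 offers its tables and listings as examples that may be changed during the analysis.

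**The concern.** The body text and the shell seem to disagree on whether a Visit 5 culture exists. If it does, it would be the latest culture in the listing, and the only efficacy table shown would ignore it. A subject negative at Visits 3 and 4 but positive at Visit 5 would stay counted as cured. In the listing, the positive result would sit beside a cure flag of Yes, if the flag is repeated as in the mock-up.

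This bears on the purpose in Section 5.1: "The results from this study will be used to determine whether the treatment can achieve mycological cure". The plan itself anticipates the problem of return, since Section 3.1 describes the last treatment as a "preventative maintenance treatment to minimize potential spore release or reinfection of the toenail during the growth of new nail". A reader who saw only Table 14.1 could take an early negative result as lasting.

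**Working it through.** **Does Visit 5 enter Table 14.1?**

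- Numerator: subjects negative for both species at Visit 3 and at Visit 4.
- Denominator: subjects who completed Visit 3 and Visit 4.

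Neither uses Visit 5, so a positive culture then moves the table by exactly 0 points. The plan states no cure rate to reproduce.

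**How late would a Visit 5 culture be?** Listing 16.2.1.2 puts Visit 3 at Day 6 or 7, Visit 4 at Day 12 ±3 (Days 9 to 15) and Visit 5 at Day 42 ±3 (Days 39 to 45). The third treatment is taken to be at Visit 3, an inference from three treatments within seven days.

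| Interval | Shortest | Longest | Nominal |
|---|---|---|---|
| Visit 4 to Visit 5 | 39 − 15 = 24 days | 45 − 9 = 36 days | 42 − 12 = 30 days |
| Third treatment to Visit 5 | 39 − 7 = 32 days | 45 − 6 = 39 days | 42 − 7 = 35 or 42 − 6 = 36 days |

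**What would a reversal be worth?** Suppose cure also required a negative Visit 5 culture, which the plan does not require. Then k reversals among N evaluable subjects would lower the percentage by 100 × k/N points. The values of k are assumed. So are the N values of 25 and 20; 30 is the planned enrolment. Every evaluable subject is assumed to have a Visit 5 culture.

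| N | k = 1 | k = 2 | k = 3 |
|---|---|---|---|
| 30 | 3.3 | 6.7 | 10.0 |
| 25 | 4.0 | 8.0 | 12.0 |
| 20 | 5.0 | 10.0 | 15.0 |

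The SAP gives no reversal rate, so nothing selects a cell. The figures are also not errors in Table 14.1: they are differences between the defined endpoint and a different one.

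**What does the Visit 5 row prove?** It is dummy data. The submission cell is blank on that row alone. As extracted, the mock entries do not line up well with their column headings: the Visit 3 mark seems to fall under Other, while the result text names another dermatophyte. Little can be inferred from individual cells.

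**Is the cure flag at Visit 5 contradictory?** The mock-up also prints Yes on the Visit 3 row, although cure cannot be known until Visit 4. The flag therefore reads most naturally as one subject-level result repeated on each post-screening row, which agrees with the footnote.

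**The case for a change.** The strongest case for a change is that two passages of one document differ, and the absent protocol does not make them agree. The Visit 5 row is filled in, not an empty placeholder. Freedom to modify shells permits a correction but does not say which passage is right, and a choice made after the cultures are known could be driven by the data. Having chosen to summarise cure by frequency and percentage, the plan would leave the latest culture out of that summary. One supportive row for subjects negative at Visits 3, 4 and 5 would cost almost nothing.

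What stands is the mismatch itself. Whoever finalises the shell will have to drop the row or have the culture named in Section 3.1, and treat the flag as the Visit 3 and 4 result. That is tidying.

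The rest does not carry. Section 3.1 summarises the design and does not say that these are the only cultures; the full sampling schedule commonly belongs to the protocol. The cure result cannot drift with the data, because its definition and denominator are fixed without Visit 5. An extra row would leave that result unchanged and repeat what the listing already shows, from a culture not shown to be taken. A positive Visit 5 culture also need not mean that the earlier result was wrong, since Section 3.1 itself allows for reinfection. Such a row is a matter of taste in display.

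**Conclusion.** No change to the plan is called for. Section 3.1 and the listing mock-up do not match on Visit 5, but this is a clerical slip or an unstated detail of the sampling schedule. It affects neither the cure definition nor the numerator or denominator of Table 14.1: the effect on the planned result is 0 points.

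The 3.3 to 15.0 points shown above apply only if a Visit 5 culture is taken, if between one and three of 20 to 30 evaluable subjects reverse, and if cure is redefined to need that culture. The SAP supports none of these conditions beyond the single mock row.

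If the culture is taken, any later positive will be visible subject by subject in the listing that feeds the table. For a 30-subject feasibility study without inference, that is adequate disclosure. This rests on the listing being produced with all cultures obtained, as Section 5.5 commits to do.
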